3.4.2. Responder Rates

The 50%, 75% and 100% responder rates will be determined as outlined in the missing data Section 2.7.2 and the endpoint definition in Section 2.2.2. The number of subjects who are responders and the rate (full analysis population as the denominator) will be summarized for each treatment group at each 4, 12, and 24 week interval. The difference in rates and associated confidence interval will also be produced. These confidence intervals will be calculated based upon the normal approximation for two independent proportions. Stratification will not be used for these intervals. The SAS procedure, Proc Freq, will be used to calculate these confidence intervals. Any interval for which the normality assumption is questionable (i.e. $np < 5$ or $nq < 5$) will be flagged.

Plots of the percent of responders across time, for each response level, will be produced. These plots will use the four week responder rates.

A p-value for the difference in rates for the key secondary endpoints will be based upon the CMH test outlined in Section 2.5.

Should the as randomized and ‘true’ values for the stratification factors differ, the as randomized values will be used within these CMH tests. The SAS procedure, Proc Freq, will be used to calculate this p-value. Cumulative distribution of the responder rate will be plotted.

3.4.2.1. Percentage of Subjects with a Migraine on the Day after Dosing

The percentage of subjects with a migraine will be summarized for each treatment group at baseline and each day from Day 0 to Day 7. A p-value for the difference from Placebo in the percentage of subjects with a migraine on the day after dosing (Day 1) will be provided. The average number of migraine hours on each of these days will also be presented.

3.4.2.2. Reduction in Migraine Prevalence

Summary tables for the reduction in migraine prevalence and change from baseline by 1 week intervals for Weeks 1, 2, 3, and 4 and treatment group will be produced. The p-value from the test outlined in Section 2.5.2 will be provided. Plots of the change in the reduction in migraine prevalence from baseline from weeks 1-4, for each response level, will be produced.

3.4.2.3. Time to First Migraine after Dosing

The analysis of the time to the first migraine after dosing endpoint will be based upon Kaplan-Meier method. The 25th percentile, 50th percentile (median), and 75th percentile, and their corresponding 95% confidence intervals will be reported for each treatment group. The percent of subjects who are migraine free at Days 1, 2, 3, 4, 5 and 6 and Weeks 1, 2, 4, 8, 12, 16, 20, 24 and the associated confidence intervals will be summarized for each treatment group. A subject will be censored for the eDiary analysis at the time of their last data entry. Kaplan-Meier plots for time to first migraine will be presented for Weeks 1-12.

3.4.2.4. Acute Migraine Medication Days

Similar outputs will be produced for the Acute Migraine Medications Days as were produced for the primary endpoint. These will include 4 week, 12 week and 24 week summary measures and the p-value from the test outlined in Section 2.5.

3.4.2.5. Health-Related Quality of Life (HIT-6)

The actual score and change from baseline for the total score will be summarized at each scheduled visit by treatment group. A shift from baseline to each scheduled visit by treatment group will be tabulated for each item. The p-value at Week 12 from the test outlined in Section 2.5 will be provided.

3.4.3. Remaining Headache and Migraine Secondary Endpoints

A summary table including confidence intervals for the treatment difference for the 4, 12, and 24 week time intervals will be produced for the remaining secondary endpoints.

Missing data rule for both Missing Data Rules provided in Section 2.7.2 will be utilized. For severe intensity and acute medication usage endpoints, the missing data rule will be applied to the numerator and denominator separately before calculating the percent.

3.4.4. Tertiary Headache and Migraine Endpoints

A summary table including confidence intervals for the treatment difference for the 4 week time intervals will be produced for headache episodes, migraine attacks, migraine symptom-free days and Most Bothersome Symptoms.

Missing data rule for Missing Data Rule 1 provided in Section 2.7.2 will be utilized for the exploratory analyses.

3.4.5. Other Secondary and Tertiary Efficacy Analyses

3.4.5.1. Most Bothersome Symptom (MBS)

The change from baseline will be summarized for MBS using the Full Analysis Population at each scheduled visit by treatment group.

3.4.5.2. Short-Form Health Survey (SF-36 v 2.0)

The actual score and change from baseline in each of the eight sections as well as the two component scores will be summarized using the Full Analysis Population at each scheduled visit by treatment group using descriptive statistics.

3.4.5.3. Health-Related Quality of Life (EQ-5D-5L)

The change from baseline will be summarized separately for each EQ-5D-5L item using the Full Analysis Population at each scheduled visit by treatment group. A shift from baseline to each scheduled visit by treatment group will be tabulated for each item.

3.4.5.4. Patient Global Impression of Change (PGIC)

The change from baseline will be summarized for PGIC using the Full Analysis Population at each scheduled visit by treatment group.

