15.6. Patient Global Impression of Change (PGIC)

Patient Global Impression of Change (PGIC)

This section to be completed by site staff

Protocol: ALD403-CLIN-011 Subject #: _____ Visit Date: _____

Visit (please check one):

Week 4 Week 8 Week 12 Week 16 Week 20
 Week 24 Week 32 or ET

Since first receiving study drug in this study, how would you describe the change (if any) in ACTIVITY LIMITATIONS, SYMPTOMS, EMOTIONS and OVERALL QUALITY OF LIFE, as related to your migraine? Choose ONE.

 Very Much Improved
 Much Improved
 Minimally Improved
 No Change
 Minimally Worse
 Much Worse
 Very Much Worse

Version Date: 16 Aug 2016

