15.7. Most Bothersome Symptom (MBS)

Most Bothersome Symptom (MBS)

This section to be completed by site staff at each visit, Screening through Week 32

Protocol: ALD403-CLIN-011 Subject #: _____ Visit Date: _____

Visit (please check one):

Screen Day 0 Week 4 Week 8 Week 12
 Week 16 Week 20 Week 24 Week 32 or ET

Most Bothersome Symptom (as noted by subject at screening visit): _____

This section to be completed by subject at each visit, Day 0 through Week 32

Since beginning this study, how would you describe the change (if any) in your most bothersome symptom? Choose ONE.

Very Much Improved
 Much Improved
 Minimally Improved
 No Change
 Minimally Worse
 Much Worse
 Very Much Worse

Version Date: 17 Aug 2016

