The number of days that subjects used acute migraine medication (i.e. triptan or ergotamine) will be summarized in 4, 12, and 24 week intervals. The 12 and 24 week results will be the average of the individual 4 week results that make up those wider intervals (e.g. the secondary endpoint of Weeks 1-12 will be the average of the Weeks 1-4, 5-8, and 9-12 results). The change from baseline for these measures will be the difference between the post baseline interval and baseline.

Migraine Free Days

The number of days between migraines are classified as migraine free days. Multiple migraine free intervals will exist for each subject. The Migraine Free Days endpoint will measure the length of these intervals. For these calculations all days between recorded migraines will be considered migraine free.

Patient Global Impression of Change (PGIC)

The PGIC includes a single question concerning the subject's impression of the change in their disease status since the start of the study. Seven responses are possible: Very Much Improved, Much Improved, Minimally Improved, No Change, Minimally Worse, Much Worse, Very Much Worse.

SF-36 Health Survey (SF-36 v2.0)

The SF-36 v2.0 is a health survey containing 36 questions consisting of eight scaled scores to measure quality of life over the past 4 weeks. The eight sections measured are vitality, physical functioning, bodily pain, general health perceptions, physical role functioning, emotional role functioning, social role functioning, and mental health. These domains are combined into the mental component score and the physical component score. Scoring software utilizing the 2016 norm-based scoring algorithm will be used to calculate the scaled score for each of the eight sections.

EQ-5D-5L

The EQ-5D-5L is a descriptive system of health-related quality of life states consisting of five dimensions/questions (mobility, self-care, usual activities, pain/discomfort, anxiety/depression) each of which can take one of five responses. The responses record five levels of severity (no problems/slight problems/moderate problems/severe problems/extreme problems) within a particular EQ-5D dimension. The EQ-5D-5L additionally includes a VAS scale. Each item will be summarized separately.

Headache Impact Test (HIT-6 v1.0)

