3.2. Definition of Baseline

Baseline assessment for migraine and headache endpoints will be based upon the data recorded in the headache eDiary during the 28 days following screening. For other variables, the baseline assessment will be the latest available valid measurement taken prior to the administration of Investigational Product. This will generally be Day 0.

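### The planned PGIC change from baseline cannot be computed, the MBS version subtracts one change rating from another, and MBS falls under an eDiary missing-data rule

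*SAP*

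**What the plan says.** The Patient Global Impression of Change (PGIC) is an other secondary endpoint and the Most Bothersome Symptom (MBS) is tertiary (SAP 2.2). Both use the same seven ordered answers, from Very Much Improved to Very Much Worse.

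- **PGIC analysis.** SAP 3.4.5.4 consists of one sentence: "The change from baseline will be summarized for PGIC using the Full Analysis Population at each scheduled visit by treatment group".
- **MBS analysis.** SAP 3.4.5.1 is worded in the same way: "The change from baseline will be summarized for MBS using the Full Analysis Population at each scheduled visit by treatment group".
- **Baseline.** SAP 3.2: "For other variables, the baseline assessment will be the latest available valid measurement taken prior to the administration of Investigational Product".
- **PGIC question.** The form in Protocol 15.6 begins "Since first receiving study drug in this study, how would you describe the change (if any". SAP 2.2.2 describes the answer as the subject's "impression of the change in their disease status since the start of the study".
- **MBS question.** The form in Protocol 15.7 asks "Since beginning this study, how would you describe the change (if any) in your most bothersome symptom". SAP 2.2.2 sets screening as the reference point.
- **Missing data.** SAP 2.7.2 makes Missing Data Rule 1 the only rule for tertiary endpoints other than Migraine Free Days, with denominators limited to subjects who completed the eDiary on at least 21 of 28 days. SAP 3.4.4 names MBS among its endpoints, plans treatment-difference confidence intervals by 4-week interval, and adds: "Missing data rule for Missing Data Rule 1 provided in Section 2.7.2 will be utilized for the exploratory analyses".

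**The concern.** A change from baseline needs a baseline value and a later value of the same status measure. PGIC has no value before dosing, and neither scale measures status: each answer is the subject's own statement of how much has changed. For PGIC, the programmer has nothing to subtract and would have to invent a rule for a listed secondary endpoint. For MBS the subtraction can be run, but the result no longer describes what the subject reported at the visit. Attaching an eDiary-completion rule to MBS adds a second problem, since MBS is a form filled in at visits and not a count of diary days. At stake are the meaning and reproducibility of two descriptive, patient-reported summaries.

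**Working it through.** The plan gives no figure to reproduce here, so the check sets schedules, forms and definitions side by side.

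**Step 1: is there a baseline?** Visits are from the schedules (Protocol section 2, SAP Table 1) and the two forms.

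| Scale | Visits at which the subject gives a rating | Ratings before first dose |
|---|---|---|
| PGIC | Weeks 4, 8, 12, 16, 20, 24, 32 or ET | 0 |
| MBS | Day 0, then the same visits as PGIC | 1 (Day 0) |

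The PGIC form has no Screening or Day 0 box, and its question cannot be answered before dosing. Under SAP 3.2 the PGIC baseline is therefore missing for every subject, and the planned quantity is undefined at all seven visits.

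For MBS, the screening visit only records which symptom it is. The first rating is on Day 0, and Protocol 10.2.6 puts all Day 0 questionnaires before the infusion. That rating meets the SAP 3.2 definition of baseline, but it is itself a rating of change since screening.

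**Step 2: what does the MBS subtraction produce?** The documents give no numeric coding. Assume 1 = Very Much Improved, 4 = No Change, 7 = Very Much Worse, and score = Week 12 rating − Day 0 rating.

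| Day 0 answer | Week 12 answer | Score |
|---|---|---|
| Much Improved (2) | Much Improved (2) | 2 − 2 = 0 |
| Minimally Improved (3) | Much Improved (2) | 2 − 3 = −1 |
| No Change (4) | Much Improved (2) | 2 − 4 = −2 |
| Minimally Worse (5) | Much Improved (2) | 2 − 5 = −3 |

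One Week 12 answer thus gets four scores. In reverse, a score of −2 arises from the (Day 0, Week 12) pairs (3,1), (4,2), (5,3), (6,4) and (7,5), so it covers Week 12 answers from Very Much Improved to Minimally Worse.

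**Step 3: how far does a mean move within one arm?** Suppose every Week 12 answer is 2, a share s answered 3 on Day 0, and the rest answered 4. The mean score is (1 − s)(2 − 4) + s(2 − 3) = −2 + s.

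| s (assumed) | Mean score | Direct rating relative to No Change |
|---|---|---|
| 0% | −2.0 | −2.0 |
| 10% | −1.9 | −2.0 |
| 20% | −1.8 | −2.0 |
| 30% | −1.7 | −2.0 |

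At s = 0 the subtraction is only a shift by a constant.

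**Step 4: does it bias the comparison of arms?** Write W for the later rating and D for the Day 0 rating. The difference in mean change is (mean W active − mean W placebo) − (mean D active − mean D placebo). D is taken before dosing in a randomised, blinded trial, so the second bracket is zero in expectation. No bias in the contrast is expected.

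**Step 5: Missing Data Rule 1 applied to MBS.** Rule 1 multiplies a result by the inverse of the diary completion rate. The SAP's example has 5 missed days: 28/23 = 1.217, which matches its 1.22. Applied to an MBS rating of 2, this gives 2 × 1.22 = 2.44, which is not a category; under this coding, missed diary days would make the symptom look worse. The 21-day denominator would drop valid ratings, collected on paper (Protocol 14.4), because of poor diary compliance. MBS is also collected at Week 32 (Day 224), but the last diary interval in SAP Table 4 ends on Day 167, so no interval exists from which to apply the rule at that visit.

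**The case against.** The strongest reply is that the wording is loose and not wrong. A PGIC answer is itself a change, so summarising the change may simply mean summarising the reported category. SAP 2.5.3 promises summary statistics for secondary endpoints, SAP 3.1 prescribes counts and percentages for categorical variables, and Protocol 13.4.2 asks for non-diary endpoints by study week. From these a sensible PGIC table could be built.

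This stands in part. A reader might infer that PGIC is left with no usable analysis; the documents do not support that, because the generic provisions are a fallback. But the SAP does not assign them to PGIC, and its PGIC-specific rule uses a term that SAP 3.2 defines in a way PGIC cannot meet. The neighbouring sections do not settle the intent: HIT-6 and SF-36 distinguish the actual score from its change, while EQ-5D-5L, which does have a baseline, also mentions only change.

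For MBS, it can be argued that subtracting a pre-dose rating removes pre-treatment change. A reader might infer that the MBS summary would misstate the treatment effect; Step 4 shows why that does not follow. What remains is that the score hides the reported category and that means within an arm may shift.

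On Rule 1, the sentence in SAP 3.4.4 speaks of exploratory analyses and does not name MBS, and a single rating offers no 28-day count to scale. However, SAP 2.7.2 covers all tertiary endpoints except Migraine Free Days, and its denominator restriction would apply to MBS even if the scaling were ignored.

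**Conclusion.** The point holds as a minor defect of specification. The PGIC rule is undefined for every subject under the SAP's own baseline definition; this needs no assumption beyond the schedule and the form. The MBS rule can be computed but gives different scores to the same answer. How much that matters depends on the share of subjects answering other than No Change on Day 0, which the documents do not give; if that share is zero, it does no harm. The coding and the 10% to 30% shares used above are illustrative assumptions. Placing MBS under Missing Data Rule 1 does not suit a paper visit rating and cannot work at Week 32.

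A reader might infer a threat to the trial's conclusions. There is none: neither scale is in the testing sequence of SAP 2.3, which treats all efficacy analyses outside that sequence as exploratory.

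**What to change.** - In SAP 3.4.5.4 and 3.4.5.1, replace change from baseline with a tabulation of the seven observed categories (n, %) by visit and arm, with no subtraction.
- Show the Day 0 MBS rating separately, labelled as a pre-dose rating.
- In SAP 2.7.2 and 3.4.4, exempt MBS from Missing Data Rule 1 and from its eDiary-based denominator. Say in 3.4.4 which MBS quantity the planned confidence interval refers to, and reconcile its 4-week intervals with the by-visit summary in 3.4.5.1.
- Reconcile the PGIC reference point: start of the study in SAP 2.2.2, first study drug on the form.

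A comparison of the proportion Much or Very Much Improved, with a confidence interval, is optional; nothing in the plan requires it.

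The cost is SAP wording only. Data collection, sample size and the testing sequence are unaffected.

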3.5. Analysis of Drug Concentrations

The concentrations of Free ALD403 will be measured in plasma from all ALD403-treated subjects using validated assay methods. The PK analysis will include evaluations of concentration-time profiles for Free ALD403 at the following times: pre-dose on Day 0, immediately post-dose (within 15 minutes of end of infusion) and Weeks 2, 4, 8, 12 (pre-dose), 24, and 32 or ET.

The concentrations of Free ALD403 will be listed and summarized by time point and dose group, and descriptive statistics will be provided. In this analysis, concentrations below the lower limit of quantification (LLOQ) will be set to zero.

Plots of the individual concentrations of ALD403 will be presented over time (linear and log scales). Plots of the mean or median concentration will be presented over time (linear and log scales). When the scale is linear, concentrations below the lower limit of quantification will be set to zero. In the log-scaled figures, concentrations below the LLOQ will be imputed as LLOQ/2. Population pharmacokinetic analysis will be performed on the results for ALD403

concentrations obtained during this study in combination with the results from other studies of ALD403 in normal subjects and migraine patients.

3.6. Analysis of Safety Endpoints

3.6.1. Adverse Events

Adverse events are collected from the time of Informed Consent through the final subject visit. The incidence of all AEs and study drug-related AEs will be tabulated by treatment received. These AEs will be classified by system organ class and preferred term using the MedDRA. For incidence reporting, if a subject reported more than 1 AE that was coded to the same preferred term/system organ class, the subject will be counted only once for that specific preferred term/system organ class. Events recorded between the time the informed consent is signed and the first Investigational Product administration will be listed.

A treatment-emergent AE (TEAE) is an AE with a start date and time on or after the date and time of the treatment.

For the purpose of inclusion in TEAE tables, incomplete AE onset and end dates will be imputed as follows:

Missing onset dates (where UK and UKN indicate unknown or missing day and month respectively):UK-MMM-YYYY: If the month and year are different from the month and year of the first dose of trial drug, assume 01-MMM-YYYY. If the month and year are the same as the first dose of trial drug month and year, and the end date (after any imputation) is on or after the first dose of trial drug, then assume the date of the first dose of trial drug. If the month and year are the same as the first dose of trial drug month, and year and the end date (after any imputation) is prior to the first dose of trial drug, then assume the end date for the onset date.

- DD-UKN-YYYY/UK-UKN-YYYY: If the year is different from the year of first dose of trial drug, assume 01-JAN-YYYY of the collected year. If the year is the same as the first dose of trial drug year, and the end date (after any imputation) is on or after the first dose of trial drug, then assume the date of the first dose of trial drug. If the year is the same as the first dose of trial drug, and the end date (after any imputation) is prior to the first dose of trial drug, then assume the end date for the onset date.

Missing end dates (where UK and UKN indicate unknown or missing day and month respectively):

- UK-MMM-YYYY: Assume the last day of the month;
- DD-UKN-YYYY/UK-UKN-YYYY: Assume 31-DEC-YYYY.

An overview of AEs, which includes subject incidence of TEAEs, study drug-related TEAEs, Serious TEAEs, TEAEs leading to study treatment interruption, TEAEs leading to study drug discontinuation and deaths will be presented.

The subject incidence of TEAEs and treatment-related TEAEs will be summarized by system organ class and preferred term.

Treatment-emergent AEs will also be summarized in a table by severity. For TEAEs presented by severity, the worst severity for each event during the clinical trial will be presented for each subject.

All AEs will be presented as a listing by subject. This listing will include the duration of the AE.

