11.1.2. Assessment of Adverse Events

The Investigator is required to monitor the occurrence of adverse events for each subject from the time of informed consent through the course of the clinical trial. Adverse events may be reported by the subject, reported by a caregiver, or reported by the investigative site through Investigator site personnel open-ended questioning, through physical examination, laboratory test, documentation in medical records, or by other means. Adverse events include:

- Any new undesirable medical experience or an unfavorable and unintended change of an existing condition that occurs during or after treatment, whether or not considered related to the Investigational Product.
- Any abnormal assessment or laboratory findings considered by the Investigator to be clinically significant. Clinically significant findings include but are not limited to those that lead to discontinuation or interruption of study treatment, require therapeutic intervention, or require a change in subject management.

A new or worsening of a pre-existing or chronic condition is considered an adverse event and must be reported as such. Medical conditions, which existed prior to the time of informed consent into the clinical trial, will not be considered an adverse event unless the condition worsens. Unchanged, chronic, non-worsening or pre-existing conditions from the time of informed consent are not adverse events and should not be recorded on the AE eCRF.

Pre-existing medical conditions of clinical significance must be included in the subject's medical history and recorded on the medical history eCRF page.

Each event recorded on the AE eCRF is required to be assessed by the Investigator with regard to the following; seriousness, severity, and relationship to Investigational Product, as outlined below.

Seriousness

An adverse event or suspected adverse event is considered serious if in the view of either the Investigator or Sponsor, it results in;

- Death
- Is life-threatening (this means that the subject is at risk of death at the time of the event; it does not mean that the event hypothetically might have caused death if it were more severe)
- Inpatient hospitalization or prolonged existing hospitalization
- A persistent or significant incapacity or substantial disruption of the ability to conduct normal life functions.
- Congenital anomaly/ birth defect

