1.2. Clinical Trial Design

This is a parallel group, double-blind, randomized, placebo-controlled trial of two infusions of ALD403 or placebo in patients with chronic migraine. Subjects who provide informed consent will be evaluated for eligibility based upon the inclusion and exclusion criteria.

Eligible subjects will be randomized 28-30 days after the screening visit and treated (first dose) on Day 0. The Day 0 visit occurs 0-8 days after randomization. Treatment includes two infusions of ALD403 or placebo administered on Days 0 and 84 (Week 12). Subjects will be followed for 20 weeks after the final dose for total study duration of approximately 36 weeks, including the screening period.

Approximately 1050 subjects will be randomized and treated. Efficacy, safety, pharmacokinetic, and immunogenicity assessments will be conducted according to the Schedule of Events presented in [Table 1](#).

Table 1: Schedule of Events and Assessment

Assessment	Screen	Rand ¹ 28-30 days after Screen	Day 0 ² Tx Within 8 days after RAND	Week 2 Day 14 -3 days	Week 4 Day 28 ± 3 days	Week 8 Day 56 ± 3 days	Week 12 Day 84 ± 3 days Tx	Week 16 Day 112 ± 3 days	Week 20 Day 140 ± 3 days	Week 24 Day 168 +7 days ³	Week 32 EOS/ET Day 224 ± 7 days
Informed Consent	X										
Inclusion/Exclusion Criteria Review	X	X	X								
Demographics	X										
Medical History	X										
Headache eDiary Data Review and Compliance Check ⁴	X	X	X	X	X	X	X	X	X	X	
Headache eDiary closeout ⁵										X	X
Height and Weight ⁶	X		X				X			X	X
Physical Exam ⁷	X		X				X			X	X
Patient Global Impression of Change (PGIC)					X	X	X	X	X	X	X
Most Bothersome Symptom (MBS)	X		X		X	X	X	X	X	X	X
Vital Signs ⁸	X		X		X	X	X	X	X	X	X
C-SSRS ^{9,10}	X		X	X	X	X	X	X	X	X	X
12-lead ECG ¹¹	X		X				X				X
Hematology, Chemistry ¹²	X		X				X				X
Serology (HIV, Hepatitis B and C)	X										
Urine Drugs Abuse Screen	X										
Urine Pregnancy (hCG) Test ¹⁰	X		X				X				X
Plasma ALD403 (PK) ¹²			X	X	X	X	X			X	X
Serum Anti-ALD403 Ab ¹²			X	X	X	X	X			X	X
SF-36, EQ-5D-5L, and HIT-6	X		X		X		X	X		X	X
AE Review	X	X	X	X	X	X	X	X	X	X	X
Concomitant Medication Review	X	X	X	X	X	X	X	X	X	X	X
Randomization		X									
ALD403/placebo administration ¹³			X				X				

Abbreviations: TX: Treatment, Rand: Randomization, EOS/ET: End of Study/Early Termination
Please refer to next page for footnotes.

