3.6.2.2. Serious Adverse Events

All SAEs will be listed and summarized in a similar manner to TEAEs.

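### The SAP defines treatment emergence by AE start time alone, so a pre-dose AE that worsens or becomes serious after the infusion can miss the TEAE tables, and the two serious-event counts can disagree

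*SAP*

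**What the plan says.** SAP 3.6.1 sets the collection period: "Adverse events are collected from the time of Informed Consent through the final subject visit". It then gives the definition: "A treatment-emergent AE (TEAE) is an AE with a start date and time on or after the date and time of the treatment". There is no clause for an AE that begins earlier and later worsens or becomes serious. For the interval before dosing it says: "Events recorded between the time the informed consent is signed and the first Investigational Product administration will be listed". The overview table in the same section has a row for serious TEAEs, and the severity table rests on the rule that "the worst severity for each event during the clinical trial will be presented for each subject".

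For serious events, SAP 3.6.2.2 says: "All SAEs will be listed and summarized in a similar manner to TEAEs". It states no limit to onset after dosing.

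On recording, Protocol 11.1.2 includes among AEs "an unfavorable and unintended change of an existing condition that occurs during or after treatment", and it also requires a worsening of a pre-existing condition to be reported as an AE. Protocol 11.1.3 lists what an AE report should contain, including an onset date, a severity and whether the event is serious. Protocol 11.1.4 has the site report an SAE by completing the AE page and marking why the event is serious.

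**The concern.** Safety against placebo is a secondary objective, and the between-arm comparison of emergent harm rests mainly on the TEAE tables. Worsening of something already present is one form that a drug effect can take. A rule based on onset alone can lose it, because an AE that started during screening keeps its pre-dose start date whatever happens to it later.

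The serious-event outputs add a second problem. The overview counts serious TEAEs, while the SAE section speaks of all SAEs. An event can satisfy one and not the other, so two tables that a reader would expect to agree need not. Two programmers working from the same text could also build different SAE tables.

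**Working it through.** There is no stated figure to reproduce. The check is the length of the exposed window, followed by a comparison of the rules.

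**Window.** SAP 1.2 gives two intervals: "Eligible subjects will be randomized 28-30 days after the screening visit and treated (first dose) on Day 0" and "The Day 0 visit occurs 0-8 days after randomization". From the screening visit, where consent is taken, to the first infusion:

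- shortest: 28 + 0 = 28 days
- longest: 30 + 8 = 38 days

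Any AE that starts in these 28 to 38 days fails the TEAE definition on its original record.

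**Four cases, taking the rules together.**

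1. *Pre-dose onset, worse after infusion, new record opened.* The new record has a post-dose start, so it is a TEAE and nothing is lost. Protocol 11.1.2 supports this route.
2. *Pre-dose onset, worse after infusion, existing record updated.* The start date is still pre-dose. The event is absent from TEAE incidence and from TEAE severity. It appears in the AE listing.
3. *Pre-dose onset, becomes serious after infusion, existing record marked serious.* It is absent from the serious-TEAE row. If SAP 3.6.2.2 is read literally, it is counted in the SAE table and the two counts differ. If SAP 3.6.2.2 is read as treatment-emergent, the counts agree, but only because the event is in neither table. If it is fatal, it can still enter the overview's deaths row, which has no treatment-emergent limit.
4. *Pre-dose onset and already serious before dosing, subject later dosed.* It is absent from the serious-TEAE row. On the literal reading of SAP 3.6.2.2 it is in the SAE table under the subject's arm; on the other reading it is listed only.

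**Which of cases 1 and 2 the documents call for.** They do not say. The Protocol 11.1.2 sentence requiring a worsening to be reported sits beside text about conditions that existed before consent. The broader bullet quoted above can cover a screening AE, but it gives no instruction to open a second record. The SAP's worst-severity rule fits severity changing within one record, though it also fits several records of the same event. The eCRF completion instructions are not part of these documents.

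**Case 3.** Protocol 11.1.4 asks for the reason for seriousness on the AE page. Nothing asks for a new record or a new onset date, so no other provision clearly cures this case.

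**The case against.** The strongest reply is that the protocol already makes a post-treatment worsening an AE in its own right. A site that reports it so creates a record with a post-dose start, and the SAP rule then picks it up. This stands for worsening: the loss is conditional on how sites record, and neither document tells them to overwrite the earlier record. It is weaker for an AE that becomes serious, where the only stated step is to mark the AE page.

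A second reply is that other outputs do not depend on the TEAE definition. This also stands. All AEs are listed by subject. The AESI tables in SAP 3.6.2.1 are defined on adverse events and cover severity, relationship and seriousness. Laboratory shifts, QTcF categories and post-baseline C-SSRS results are separate from AE onset. SAP 3.6.1 also tabulates AEs overall, although its sentence on listing pre-dose events leaves the scope of that table unclear. None of these makes the TEAE and SAE tables agree.

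A third reply is that the wording of SAP 3.6.2.2, which likens the SAE summary to the TEAE summary, together with the rule that pre-dose events are listed, allows a treatment-emergent SAE table. That reading is possible, but the stated scope is every SAE. Restriction to the safety population removes only subjects who were never treated.

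A reader might infer that every screening AE that worsens is lost from every TEAE table, or that the SAE table certainly includes pre-dose events. The documents support neither; both are possible outcomes of unsettled wording.

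**Conclusion.** The point holds as a definition that can give wrong or inconsistent counts. An AE with onset between consent and first infusion that worsens or becomes serious afterwards can be left out of TEAE incidence, TEAE severity and the serious-TEAE row. The serious-event count in the overview can then differ from the SAE summary. The conclusion assumes that at least some sites update an existing record instead of opening a new one.

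The size cannot be derived from the documents. It is tempting to read the time share as an event share: with follow-up to Day 224, the pre-dose period is 28/(28 + 224) = 11.1% to 38/(38 + 224) = 14.5% of collection time. That would be the pre-dose share of SAEs only if they arose at a uniform rate among subjects who went on to be dosed. Eligibility is reviewed again at randomization and on Day 0. Exclusion criterion 11 removes subjects with a clinically significant concurrent condition in that period, and Protocol 10.3 says that ineligible subjects are not dosed. The true share among treated subjects is therefore probably lower, and the number of affected subjects is probably small.

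The safety summaries are descriptive. The primary and key secondary analyses, the power and the type I error are not affected.

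**What to change.** In SAP 3.6.1, define a TEAE as an AE with onset on or after the start of the first infusion, or an AE with earlier onset that increases in severity or becomes serious on or after that time. Naming the first infusion also settles which of the two infusions the current definition means.

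In SAP 3.6.2.2, limit the SAE summary table to treatment-emergent SAEs under that definition and keep pre-dose SAEs in the listing. The SAE table and the serious-TEAE row of the overview then count the same events.

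This is a cheap improvement. It costs two changes of wording, one programming flag, and site queries for pre-dose AEs where the date of a severity or seriousness change was not recorded.
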